2.3 Potential Risks and Benefits

2.3.1 Potential Risks

The risks of participating include a breach of confidentially, side effects from taking the IP, discomfort when completing blood tests and/or the nature of the assessments involved in the study, including those conducted by the researcher as well as completed by the participants.

Participant's personal details will be collected during the baseline session of study (for contact purposes thereafter) and subsequent data will be de-identified. Although every effort will be made to maintain the anonymity of participants, a breach of confidentially is possible. See section 11.3 for further details regarding confidentially.

NAC may induce gastrointestinal side effects including mild abdominal pain or discomfort, heartburn, diarrhea, flatulence, nausea and cramps (Deepmala et al., 2015; Sarris et al., 2015).

Headaches, dizziness and skin rashes have also been reported in previous clinical studies (Ghanizadeh et al., 2017). However, specific to psychiatric research studies, only a small minority of participants have withdrawn due to side effects of NAC including a skin rash (n = 1), aggression (n = 1), severe heartburn (n = 1), neutropenia (with 6 grams of NAC, resolved when dose reduced to 2.4g; n = 1) and sensorineural deafness (n = 1) (Deepmala et al., 2015)

Participants may experience discomfort or bruising when having their blood taken during the study. The blood vessel may swell, or blood may clot in the blood vessel. Rarely, there could be a minor infection or bleeding.

Given that participants will be reviewing their mental, general and physical health in each of the study visits, some may find this psychologically distressing. To minimize these risks, all RAs involved in the assessment of participants will ensure that participants are adequately supported outside of the study, for example, advising them to maintain contact with their GP, psychiatrist and/or psychologist as required. In addition, participants who experience significant worsening in their mental health will be withdrawn from the study and referred for treatment. Further, during the informed consent discussion at baseline, the voluntary nature of the study and a participant's right to withdraw at any stage of the study will be highlighted.

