5.8 Baseline 1 session

Individuals that attend the baseline 1 session will meet with an RA who will discuss the PICF for the research study. An opportunity will be provided for the individual to ask any questions or raise any queries before signing the consent form. Consenting participants will be asked to provide demographic information, current and previous medications, a medical history as well as caffeine,

alcohol and drug intake over the last 3-months. A detailed description of the participants OCD, and any co-morbid mental health conditions, will be asked including its suspected onset, time of diagnosis, presentation and treatments employed since its occurrence. The Y-BOCS symptom checklist will then be administrated by the RA to determine the participant's current and most prominent obsessive and compulsive symptoms, as well as identifying symptoms experienced previously. The RA will then administer the Y-BOCS severity scale (based on the most prominent symptoms identified on symptom checklist) to ascertain the current severity of the OCD and determine eligibility. If eligible (scoring ≥16 and ≤31 on the Y-BOCS), the RA will administer the Y-BOCS question 11 to determine the participant's insight regarding their OCD symptoms, followed by the SIGHD-17. In cases where individuals do not meet me the inclusion criterial for the study, they will be outlined the reasons why and reimbursed \$20 for their time. Referral to appropriate treatment will be advised where necessary, for example, back to their treating doctor or OCD support groups such as ARCVic. If the individual does meet eligibility criteria for the study thus far, they will be asked to complete the DOCS, BAI, BIS-11, SDS, PGI-S and WHOQOL-BREF. Participants may complete these self-reporting questionnaires on site or, if preferred, they may be taken home to complete. An appointment will be made to attend the baseline 2 session to complete remaining screening assessments and return completed self-reported questionnaires (if applicable). This appointment will ideally take place within the next 7 days where possible, however, if 7+ days later, the Y-BOCS will be re-administrated at the start of the baseline 2 session to re-assess eligibility.

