5.10 Follow-up visits

Participants will be required to attend follow-up visits at Week-4, 8, 12, 16, 20 and 24. In these sessions, participants will be asked to provide an overview since their last visit, particularly any noticeable changes in their OCD, mental health, functioning and/or quality of life. Changes in treatment (pharmacological and/or psychological), drug and alcohol consumption, medical conditions and the occurrence of side effects, if any, will also be ascertained. The Y-BOCS symptom checklist will be re-administrated by the RA to identify current obsessive and compulsive symptoms, followed by Y-BOCS severity scale (including question 11 regarding insight) and SIGHD-17. At each follow-up visit, the participant will also be asked to complete the DOCS, BAI, SDS, PGI-S, PGI-I and SAFTEE. Upon conclusion of each follow-up visit, the participants blood pressure will be taken and the CGI-I and CGI-S completed by the RA. In addition, at Week-12 and Week-20, the WHOQOL-BREF will also be completed by the participant.

Participants will also be reimbursed for travel expenses totaling \$140-\$160 in the form of Coles/Myer gift cards (\$20 at each scheduled visit; \$160 in total if all study visits are completed and if the baseline sessions are completed on separate days, reflecting additional travel costs incurred to the participant).

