7 ASSESSMENT OF SAFETY

7.1 Methods and Timing for Assessing, Recording, and Analyzing Safety Parameters

7.1.1 Adverse Events

ICH E6 defines an adverse event (AE) as any untoward medical occurrence in a patient or clinical investigation subject administered a pharmaceutical product regardless of its causal relationship to the study treatment. An AE can therefore be any unfavorable and unintended sign (including an abnormal laboratory finding), symptom, or disease temporally associated with the use of the IP. The occurrence of an AE may come to the attention of study personnel during or by communication in between study visits or the participant presenting for medical care.

[name], [name] and [name] will be available for medical supervision relating to the participants in the study at The Melbourne Clinic. [name] and [name] will provide medical supervision at The Royal Brisbane and Women's Hospital and [name] at Western Sydney University.

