7.2.2 Adverse Events

At the beginning of every follow-up visit, participants will be questioned non-specifically for any adverse events (AEs) as well as asked to complete a purpose-designed Symptom Checklist (the Systematic Assessment for Treatment Emergent Events; SAFTEE) to determine if a participant experienced an AE. Any verbally reported AEs or any symptoms on the SAFTEE marked as causing significant distress, including local and systemic reactions not meeting the criteria for a SAE, will be recorded in the participant's CRF. The information recorded in the CRF will be based on signs and symptoms reported by the participant or observed by the investigators. All AEs will be discussed with the study investigators in weekly teleconferences relating to the progress of the study and any necessary intervention for AEs will be decided by the medical investigators.

A description of each event, date and time of onset, assessment of severity, suspected relationship to study product (assessed only by those with the training and authority to make a diagnosis, which would include an MD or psychiatrist), and time of resolution/stabilization of the event. All AEs occurring during the study must be documented appropriately regardless of relationship. All AEs will be followed to adequate resolution, and if a participant experiences an AE or an SAE during the treatment period that has persisted through to the last testing day, consent will be requested for continued contact with the participant until the AE or SAE has fully resolved. The status of the participant's condition will be recorded in their CRF each time contact is made.

Any medical condition that is present at the time that the patient is screened should be recorded in their medical history and not reported as an AE. However, if this condition deteriorates at any time during the study, it should be recorded as an AE.

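### The SAFTEE distress threshold conflicts with the protocol's own AE definition, and without a pre-dose SAFTEE the emergence of a checklist symptom rests on medical history alone

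*Protocol*

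**What the plan says.** Section 7.2.2 (Adverse Events) has participants asked an open question about AEs at each follow-up visit and then complete the SAFTEE, whose stated purpose is to determine whether an AE occurred. Two routes lead to the CRF: AEs that the participant reports verbally, and "any symptoms on the SAFTEE marked as causing significant distress". The verbal route has no severity threshold; the checklist route has one.

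Three other statements bear on this:
- Section 7.1.1 defines an AE as "any unfavorable and unintended sign (including an abnormal laboratory finding), symptom, or disease temporally associated with the use of the IP", among other wording, with no reference to distress.
- Section 7.2.2 also says "All AEs occurring during the study must be documented appropriately regardless of relationship".
- Section 7.2.3 grades AEs from Mild upwards, and Mild covers events that do not disturb daily activities.

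Section 2.3.1 gives the expected profile: "NAC may induce gastrointestinal side effects including mild abdominal pain or discomfort", with other gastrointestinal complaints.

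On timing, the SAFTEE row of the Assessment Schedule is blank at Baseline 1 and Baseline 2 and marked from Week 4 to Week 24. The Baseline 1 self-report pack in section 5.8 does not include it: "they will be asked to complete the DOCS, BAI, BIS-11, SDS, PGI-S and WHOQOL-BREF". Section 5.9 (Baseline 2) does not mention it either. For what was present before treatment, 7.2.2 relies on medical history: a medical condition present at screening is entered there and becomes an AE only if it deteriorates.

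**The concern.** A checklist earns its place beside an open question by picking up symptoms that participants do not volunteer. The distress threshold applies to exactly those symptoms. Since the side effects expected of NAC include mild gastrointestinal ones, the threshold falls where the checklist should add most. A symptom that misses the AE record also has no entry for onset, severity, suspected relationship or resolution, all of which 7.2.2 wants.

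The missing baseline is a separate problem. The SAFTEE is named as an instrument for treatment-emergent effects, yet it has no pre-dose value. The other repeated self-report scales (DOCS, BAI, SDS, PGI-S) do have one. The inclusion criteria (4.1) require psychotropic medication, so symptoms before the first dose are plausible, though the protocol gives no rate for them. Without a like-for-like baseline, a prompted answer at Week 4 has to be compared with a history that was taken without the same list. No later analysis can recreate that baseline.

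**Working it through.** The protocol states no safety rate, power or test for AEs, so there is no figure to reproduce. The check is mainly of the text.

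**Step 1: follow one mild symptom through the rules.** Suppose a participant has mild nausea that began on treatment.
- Mentioned to the research assistant: recorded under the verbal route, then graded Mild.
- Ticked on the SAFTEE, not voiced, not marked as significantly distressing: an AE under 7.1.1, and one that 7.2.2 says must be documented, but the recording sentence of 7.2.2 does not require a CRF entry.

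The second case is the gap. Staff who follow the recording sentence literally depart from the definition.

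**Step 2: follow one pre-existing symptom.** Suppose mild nausea was present before dosing.
- Captured in medical history: 7.2.2 keeps it out of the AE record unless it worsens.
- Not captured, because nobody asked item by item: it first appears on the Week 4 SAFTEE, with nothing on the same instrument to show whether it is new, unchanged or worse.

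**Step 3: illustrate the size.** Inputs: 100 per arm (section 8.1); two-sided alpha 0.05. Assumed, not in the documents: true emergent rates of 10% on placebo and 25% on NAC among those free of the symptom. Power = Φ((d − 1.96·SE0)/SE1), where d is the difference, SE0 uses the pooled rate and SE1 the separate rates.

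*Incomplete recording, equal in both arms.*
- All events recorded: d = 0.15, SE0 = √(0.175 × 0.825 × 2/100) = 0.0537, SE1 = √((0.10 × 0.90 + 0.25 × 0.75)/100) = 0.0527; power 80%.
- 75%, 50% or 25% of events recorded: power 66%, 47% or 25%.

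*Pre-existing symptoms in a share b of each arm.* If they cannot be separated, the observed rates are b + (1 − b) × 0.10 and b + (1 − b) × 0.25. With a baseline form, emergent cases per whole arm are (1 − b) × 0.10 and (1 − b) × 0.25. The difference is (1 − b) × 0.15 either way; only the precision changes. For b = 0.30:
- Not separated: 37.0% v 47.5%, d = 10.5 points, SE1 = √((0.37 × 0.63 + 0.475 × 0.525)/100) = 6.9 points.
- Separated: 7.0% v 17.5%, d = 10.5 points, SE1 = √((0.07 × 0.93 + 0.175 × 0.825)/100) = 4.6 points.

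| b | Difference (points) | Power, not separated | Power, separated |
|---|---|---|---|
| 0.10 | 13.5 | 59% | 75% |
| 0.20 | 12.0 | 43% | 69% |
| 0.30 | 10.5 | 32% | 62% |
| 0.40 | 9.0 | 25% | 55% |

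The not-separated column is a worst case: it supposes that medical history identifies none of the pre-existing symptoms and that the distress threshold removes none.

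**The case against.** The strongest reply is that the checklist is only the second net. Verbally reported AEs are recorded at any severity. Section 5.10 adds that "the occurrence of side effects, if any, will also be ascertained" at follow-up visits. Tolerance is checked by phone 7 to 10 days after Baseline 2 (5.9) and one week after any titration (5.2), and participants are told to report AEs promptly (7.2). Sub-threshold answers also stay on the completed forms. This stands: a reader might infer that mild NAC effects are lost, and the documents do not support that. Only symptoms ticked and never voiced are at risk, and what they risk missing is the AE entry.

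A reader might also infer that pre-existing symptoms are counted as emergent. Section 7.2.2 says the opposite for conditions present at screening. Baseline 1 also gives the SIGHD-17 and BAI, which prompt for some bodily symptoms. What remains is narrower: the rule is written for medical conditions, and no baseline procedure covers the SAFTEE list.

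The Mild grade does not by itself contradict the threshold, because a verbally reported event can be graded Mild, and the all-AEs sentence is worded mainly about causality. The clear conflict is with the definition in 7.1.1.

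Finally, AEs are neither a primary nor a secondary outcome, and how checklist data are tabulated can be left to an analysis plan. That is fair for tabulation. It does not cover what is collected before dosing or what staff enter in the CRF.

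**Conclusion.** The point holds in limited form, as something the protocol should correct. The recording sentence in 7.2.2 is inconsistent with 7.1.1 and with the duty in 7.2.2 to document all AEs, so mild symptoms known only from the checklist can miss the AE record. The SAFTEE has no pre-dose value, so emergence of its symptoms depends on a history that does not cover the list.

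It is tempting to conclude that tolerability will look better than it is. The documents do not support this. The threshold lowers recorded rates, while unseparated pre-existing symptoms raise them. Randomisation balances pre-existing symptoms in expectation, so neither arm is systematically favoured. The supportable consequence is higher background rates and less precise comparisons.

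The size is unknown. The illustrated losses rest on assumed rates, equal recording in both arms and, for the baseline part, no help from medical history. The SAFTEE response scale is not described, so how far the threshold reaches beyond mild symptoms cannot be judged.

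**What to change.** 1. Add the SAFTEE before the first dose, in the Baseline 1 or Baseline 2 self-report pack, and amend the Assessment Schedule and section 5.8 or 5.9 to match.
2. Reconcile 7.1.1, 7.2.2 and 7.2.3 so that a SAFTEE symptom that is new or worse than baseline is recorded as an AE and graded. The distress rating then informs the grade and does not decide entry.
3. For participants already enrolled without a baseline form, report SAFTEE items at all levels by arm and state the limitation.

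The cost is one short extra form per new participant, more AE entries to process, and a wording amendment. Sample size and the efficacy analysis are unaffected.

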7.2.3 Severity of Event

To quantify intensity, all AEs will be graded by the following:

- Mild: events require minimal or no treatment and do not interfere with the patient's daily activities.
- Moderate: events result in a low level of inconvenience or concern with the therapeutic measures. Moderate events may cause some interference with functioning.
- Severe: events interrupt a patient's usual daily activity and may require systemic drug therapy
 or other treatment. Severe events are usually incapacitating.
- Life threatening: any adverse drug experience that places the patient or subject, in the view of the investigator, at immediate risk of death from the reaction as it occurred, i.e., it does not include a reaction that had it occurred in a more severe form, might have caused death.

Changes in the severity of an AE should be documented to allow an assessment of the duration of the event at each level of intensity to be performed. Adverse events characterized as intermittent require documentation of onset and duration of each episode.

Version 7.0 12 DEC 2018

8 STATISTICAL CONSIDERATIONS

8.1 Sample Size Considerations

A sample size of 200 participants (100 participants in each arm) are to be recruited and intention-to-treat principles will be applied to all data. A large sample of 200 participants is powered to detect a potential small to moderate effect size (f = 0.15) difference between NAC and placebo beyond treatment as usual, approximating a clinically significant 3 point reduction on the YBOCS (using all post-baseline data via intention-to-treat analysis). Based on an ANOVA model over seven time-points, a two tailed analysis with alpha=0.05, beta=0.80, and a critical F of 3.78; 200 participants (not including drop-outs) are required to detect a small to moderate effect size difference in Y-BOCS scale score between treatment and placebo.

The primary efficacy analysis will assess mean treatment group differences for the primary outcome measure (Y-BOCS) using a mixed-effects model, repeated measures approach (MMRM). Results from the analysis of dichotomous data (e.g. demographics data) will be presented as proportions with 95% confidence interval, and Fisher's Exact *p*-value where appropriate. Analysis of covariance (ANCOVA) will also be used to compare differences between treatment means in changes from baseline to week 20 last observation carried forward (LOCF) endpoint. The ANCOVA model will assess confounding covariates including intervention type (medication or psychological care), as well as age, gender, weight, physical activity levels, smoking and alcohol consumption.

Non-parametric statistics will be used when assumptions for parametric methods are violated. Effect sizes will be calculated using Cohen's d. All tests of treatment effects will be conducted using a two-tailed alpha level of 0.05 and 95% confidence intervals. Data will be analysed via SPSS 23.0.

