3 OBJECTIVES

3.1 Study Objectives

This study seeks to elucidate the benefits of NAC augmentation (2-4 grams/day) compared to placebo in the treatment of OCD, in a 20-week, multicentre, randomised, double-blind, placebo controlled trial, with an additional 4-week, single blinded placebo run-out. The purpose of including a 4-week, placebo-run out is to asses any withdraw effects and/or sustained response of the NAC. It is hypothesised that NAC will be superior over placebo for improving OCD symptoms as measured by a reduction in Y-BOCS scores from baseline against each subsequent time point (W4, W8, W12, W16, W20 and W24). Additional benefits are anticipated for relieving anxiety as well as improving mood, functioning and overall quality of life. In addition, we will analyse the presence of single nucleotide polymorphisms (SNPs) related to glutamate and glutathione activity, which may serve as a predictor of treatment response to NAC in some individuals.

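### The 80% power in section 8.1 belongs to a treatment difference averaged over seven time-points; it does not cover the visit-by-visit hypothesis of section 3.1 or the week-20 ANCOVA

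*Protocol*

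**What the plan says.** Section 8.1 plans 100 participants per arm and describes the trial as "powered to detect a potential small to moderate effect size (f = 0.15) difference between NAC and placebo", which it equates to "approximating a clinically significant 3 point reduction on the YBOCS (using all post-baseline data via intention-to-treat analysis". The calculation is introduced with "Based on an ANOVA model over seven time-points, a two tailed analysis with alpha=0.05", followed by "beta=0.80, and a critical F of 3.78" (the 0.80 is evidently power), and concludes that "200 participants (not including drop-outs) are required to detect a small to moderate effect size difference in Y-BOCS scale score between treatment and placebo". No SD, between-visit correlation or drop-out rate is given.

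The same section names an MMRM of mean group differences in Y-BOCS as the primary efficacy analysis, without specifying a visit or contrast. It adds an ANCOVA that will "compare differences between treatment means in changes from baseline to week 20", using LOCF. The covariates listed for that ANCOVA do not include baseline Y-BOCS.

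Section 3.1 states the hypothesis as superiority of NAC "as measured by a reduction in Y-BOCS scores from baseline against each subsequent time point", and lists weeks 4, 8, 12, 16, 20 and 24.

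**The concern.** Power belongs to a particular contrast. Averaging a participant's repeated scores reduces variance, so a test of the average needs fewer participants than a test at one visit for the same standardised difference. If N = 200 depends on that gain, the 80% does not transfer to a comparison at week 20 or at any other single visit.

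A reader of sections 3.1 and 8.1 together would take 80% as the power for the hypothesis as written. If the true visit-level power is lower, a non-significant week-20 result would be read as stronger evidence against a small-to-moderate effect than it is.

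**Working it through.** **Inputs from the protocol.** N = 200 (100 per arm); f = 0.15, so d = 2f = 0.30 for two equal groups; m = 7 time-points; two-sided alpha 0.05; power 0.80. The visit schedule makes the seven time-points baseline plus six follow-up visits.

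**Assumed input.** A common between-visit correlation rho, which the protocol does not state.

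**Step 1: reproduce N = 200.** For the between-groups effect in a repeated-measures ANOVA, lambda = f²·N·m / (1 + (m − 1)·rho), with 1 and N − 2 degrees of freedom. At rho = 0.5:

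lambda = 0.0225 × 200 × 7 / (1 + 6 × 0.5) = 31.5 / 4 = 7.875, power 79.7%; 80% is reached at N = 202.

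The alternatives do not come close to 200:
- Group-by-time interaction (f = 0.15, m = 7, rho = 0.5): N = 46.
- Two-group comparison at one visit: N = 352.

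So the planned N matches the averaged between-groups test. Solving back, power of 78–82% at N = 200 requires rho between 0.53 and 0.46. The printed critical F does not match this routine, since F(1,198) is 3.889. That is a separate discrepancy and is not used here.

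**Step 2: power at one visit, same d and N, no drop-out.** Two-sample noncentral t with 198 degrees of freedom and noncentrality 0.30 / (k·√(2/100)). The SD factor k is √(2(1 − rho)) for unadjusted change and √(1 − rho²) with baseline as covariate. At rho = 0.5:
- Change: k = 1, noncentrality 2.12, power 56.0%.
- Baseline-adjusted: k = 0.866, noncentrality 2.45, power 68.4%.

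| rho | Change | Baseline-adjusted | Averaged ANOVA of step 1 |
|---|---|---|---|
| 0.3 | 43% | 60% | 92% |
| 0.4 | 49% | 63% | 86% |
| 0.46 | 53% | 66% | 82% |
| 0.5 | 56% | 68% | 80% |
| 0.53 | 59% | 70% | 78% |
| 0.6 | 66% | 75% | 74% |
| 0.7 | 78% | 84% | 69% |

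At rho = 0.5, 80% power at one visit would need N = 352 (change) or 264 (baseline-adjusted).

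**Step 3: an averaged MMRM contrast.** For the mean of six post-baseline visits at rho = 0.5, the variance of the mean is (1 + 5 × 0.5)/6 = 0.583.
- Change from baseline: 0.583 + 1 − 2 × 0.5 = 0.583, power 78.9%.
- Baseline as covariate: 0.583 − 0.25 = 0.333, power 95.5%.

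**Step 4: what d = 0.30 refers to.** Randomisation makes the expected baseline difference zero.
- If 0.30 is the difference in the seven-point mean, the post-baseline difference is 0.30 × 7/6 = 0.35. Single-visit power at rho = 0.5 is then 69% (change) or 81% (baseline-adjusted).
- If 0.30 is the post-baseline difference, the seven-point mean carries f = 0.15 × 6/7 = 0.129. The formula of step 1 then gives lambda = 5.79 and 67% power, not 80%.

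**Step 5: the 3-point target.** Three points at d = 0.30 implies SD = 3/0.30 = 10. Assuming other SDs with rho = 0.5, single-visit power for 3 points is:

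| SD | Change | Baseline-adjusted |
|---|---|---|
| 6 | 94% | 98% |
| 7 | 85% | 94% |
| 7.5 | 80% | 90% |
| 8 | 75% | 86% |
| 10 | 56% | 68% |

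**The case against.** The strongest reply is that the primary analysis is the MMRM, that 8.1 links the powered effect to all post-baseline data, and that the ANCOVA is only additional. Sizing on pooled visits is consistent with that, and the MMRM contrast may properly be specified in an SAP that is not shown. This stands. A reader might infer that the primary test has only 56–68% power, but the protocol does not support that: it names no single-visit MMRM contrast, and step 3 shows an averaged one at or above the stated level when rho is 0.5.

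A second reply is that rho is back-solved, not stated, and that the result moves with it. This also stands, so the result has to be given as a range. A correlation of 0.7 would bring baseline-adjusted power at one visit to 84%, but the sizing formula would then give only 69%. A baseline-to-week-20 correlation that differs from the other between-visit correlations could change the picture, which is one more reason to state the assumption.

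Third, on the seven-point-mean reading of d (step 4) the baseline-adjusted shortfall disappears, and for a 3-point effect with SD of 7.5 or less single-visit power is at least 80%. Entry scores of 16 to 31 limit the baseline SD to about (31 − 16)/2 = 7.5, though the post-baseline SD is not given. So the shortfall applies to d = 0.30 at a visit and does not automatically apply to 3 points.

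Finally, a reader might take section 3.1 to require success at all six visits and infer very low power. No passage sets that requirement, and week 24 follows four weeks of placebo in both arms, so no such figure should be used.

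None of these replies makes the 80% apply to the visit-by-visit hypothesis that section 3.1 states.

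**Conclusion.** The point holds in a limited form. N = 200 at 80% power is not an arithmetic error for an average over seven time-points with rho near 0.5, but the unqualified 80% does not cover the comparisons at single visits in section 3.1 or the week-20 ANCOVA.

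Taking d = 0.30 at the visit, with 100 per arm, no drop-out and rho of 0.46–0.53, the chance of missing the effect is about 41–47% for unadjusted change and 30–34% with baseline adjustment, against the 20% implied. Over rho of 0.3–0.7 single-visit power spans 43–78% and 60–84%. Since baseline Y-BOCS is not among the listed ANCOVA covariates, the ANCOVA as written sits nearer the lower of the two sets of figures. Whether the primary MMRM falls short depends on a contrast the protocol does not name.

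**What to change.** Keep N = 200 and revise section 8.1:

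1. State that the 80% at f = 0.15 refers to the treatment difference averaged over visits, give the assumed between-visit correlation, and say whether baseline is one of the seven time-points.
2. Add the power for the visit-level contrast, for example week 20, as a range with its assumptions shown: at d = 0.30, and for 3 points under a stated SD, each with and without baseline adjustment.
3. Remove the implication that 200 participants give 80% power for the visit-by-visit hypothesis in section 3.1.

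The cost is a few sentences and no additional participants. The drawback is that the stated power for visit-level comparisons becomes less favourable.
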